5.3.5. Subject Replacement

Subjects who withdraw, or are withdrawn or terminated from this trial, or are lost to follow-up after signing the ICF and randomization, but before receipt of any doses of vaccine will be replaced. Subjects who do not receive protocol-specified subsequent doses of vaccine may be replaced following written approval of the sponsor (Section 5.3). Subjects who are discontinued or withdraw from this trial will be replaced irrespective of the dose group to which they were

assigned, and replacement subjects will be assigned according to usual enrollment/randomization procedures.

5.3.6. Termination of Study

If this trial is prematurely terminated by the sponsor, any regulatory authority, or the investigator for any reason, the investigator will promptly inform the subjects and assure appropriate therapy or follow-up for the subjects, as necessary. The investigator will provide a detailed written explanation of the termination to the IRB/IEC.

6. STUDY INTERVENTION/INVESTIGATIONAL PRODUCT

6.1. Study Product Description

ChAd155-RG Vaccine

The ChAd155-RG Vaccine consists of a replication-defective group C ChAd, ChAd155, expressing RG under the control of the CMV promoter. The RG sequence cloned into the ChAd155 vector is a medoid, a natural viral strain with the highest average percent of amino acid identity among all RG sequences annotated in the NCBI database. The selected RG (NCBI strain AGN94271) shares an average 94% percent identity to the RGs in current vaccines.

RABAVERT Vaccine

The RABAVERT Vaccine is an inactivated, purified chick embryo cell vaccine (PCECV). It consists of lyophilized rabies virus (strain Flury LEP) that has been propagated in chicken fibroblasts, inactivated with β -propiolactone, and concentrated and purified by centrifugation

Placebo

The placebo is 0.9% Sodium Chloride, USP injection.

6.1.1. Acquisition

ChAd155-RG and RABAVERT will be provided by GSK Vaccines under agreement with DHHS, and will be supplied through DMID CMS to the site before the start of this trial upon request and with prior approval from DMID. Should the site PI require additional vaccine during this trial, further instructions are provided in the MOP.

Placebo

Normal saline will be used as the placebo, and will be provided by DMID Clinical Materials Services (CMS, Fisher BioServices

6.1.2 Formulation, Packaging, and Labeling

ChAd155-RG Vaccine

The purified ChAd155-RG bulk drug substance is processed as follows to obtain drug product: Purified ChAd155-RG drug substance is diluted in buffer A 195 (Tris base 10mM, NaCl 75 mM, L-Histidine 10mM, MgCl₂ 1 mM, EDTA 0.1 mM, Polysorbate 80 0.02% (w/v), sucrose 5% (w/v), ethanol 0.5% (v/v), HCl for adjustment to pH 7.4). It then undergoes sterile filtration and

is then transferred into final containers. The ChAd155-RG drug product is a liquid formulation contained in vials. It is presented as a sterile suspension in a 3-mL clear glass, stoppered vial, with a 1-mL extractable volume (nominal single dose).

The vaccine is supplied as a single 1mL-dose and is formulated without preservative.

The study product will be labelled according to manufacturer specifications or regulatory specifications and include the statement “Caution: New Drug-Limited by Federal Law to Investigational Use.”

RABAVERT Vaccine²³

RABAVERT is a freeze-dried vaccine obtained by growing the fixed-virus strain Flury LEP in primary cultures of chicken fibroblasts. The virus is inactivated with β -propiolactone, processed by zonal centrifugation, and then lyophilized after adding a stabilizer solution consisting of buffered polygeline and potassium glutamate. One dose of reconstituted vaccine contains \leq 12 mg polygeline (processed bovine gelatin), \leq 0.3 mg human serum albumin, 1 mg potassium glutamate, and 0.3 mg sodium EDTA. Small quantities of bovine serum (originating from the US, Australia, and New Zealand) are used in the cell culture process; ovalbumin content is \leq 3 ng/dose (1 mL), based on ELISA. Antibiotics (neomycin, chlortetracycline, amphotericin B) added during cell and virus propagation are largely removed during subsequent steps in the manufacturing process; thus, in the final vaccine, neomycin is present at \leq 10 μ g, chlortetracycline at \leq 200 ng, and amphotericin B at \leq 20 ng per dose. Rabavert is supplied in a package that contains a vial of the freeez-dried vaccine, a syringe containing 1 mL of sterile diluent (sterile water for injection), a sterile needle for reconstitution, and a sterile needle suitable for IM injection.

The study product will be labelled according to manufacturer specifications or regulatory specifications and include the statement “Caution: New Drug-Limited by Federal Law to Investigational Use.”

Placebo

Placebo will be supplied as 0.9% Sodium Chloride Injection, USP which is a colorless, sterile, nonpyrogenic, isotonic solution of sodium chloride and water for injection (WFI). Each mL contains supplied chloride 9 mg. It contains no bacteriostatic, antimicrobial agent, or added buffer and is supplied only in single-dose containers. The placebo, 0.9% Sodium Chloride, contains no preservatives. The solution may contain hydrochloric acid and/or sodium hydroxide for pH adjustment (pH 5.3 [4.5 to 7.0]).

6.1.3 Product Storage and Stability

ChAd155-RG Vaccine

The vaccine product requires storage at $\leq -60^{\circ}\text{C}$

The stability of ChAd155-RG final container lots will be followed for up to 60 months at the recommended storage condition of $\leq -60^{\circ}\text{C}$.

RABAVERT Vaccine²³

RABAVERT contains no preservative, and should be stored protected from light at 2°C to 8°C (36°F to 46°F). After reconstitution with the supplied sterile diluent (water for injection), the vaccine should be used immediately (as defined in the MOP). The reconstituted vaccine is a clear-to-slightly opalescent, colorless-to-slightly pink suspension. The vaccine may not be used after the expiration date given on package and container.

Placebo

0.9% Sodium Chloride, USP injection must be stored at 20°C to 25°C (68°F to 77°F) [See USP Controlled Room Temperature; excursions between 15°C and 30°C (59°F and 86°F) are permitted]. See protocol-specific MOP for further instructions..

Additional information

All vaccines will be stored in the site research pharmacy. The temperature of the storage unit will be continuously monitored and recorded during this trial per the site's SOPs, and documentation will be maintained. If the temperature fluctuates outside of the required range, the affected study product(s) will be quarantined at the correct storage temperature and labeled "Do Not Use" (until further notice). The pharmacist will alert the site PI and study coordinator if the temperature fluctuates outside of the required range. If the temperature fluctuates outside of the required range, including accidental deep-freezing or disruption of the cold chain, the affected vaccine(s) will not be administered. The site PI or responsible person should immediately contact the DMID Product Support Team at [contact] and DMID Clinical Project Manager (CPM) for further instructions before any additional study vaccines are administered. Based on the information collected, DMID and/or the manufacturer will determine whether the affected vaccine(s) can be used. If it cannot be used, the site will receive specific instructions on how to return the affected vaccine(s) to DMID CMS or destroy it on site. Additional instructions for quarantine are provided in the MOP.

Stability studies to support study vaccine storage conditions have been conducted. The sponsor will continue to monitor the stability of the vaccines and will alert the site if a lot is nearing the end of its anticipated shelf life.

6.2. Dosage, Preparation and Administration of Study Intervention/Investigational Product

ChAd155-RG Investigational Vaccine

The ChAd155-RG candidate vaccine is formulated without preservative and is presented as a sterile suspension in a 3-mL clear glass, stoppered vial, at a concentration of 1.3×10^{11} vp/mL.

The dosages of ChAd155-RG to be used in this study are: 5×10^{10} vp (low dose) and 1×10^{11} vp (high dose). These dosages will be prepared at site's pharmacy. See the MOP for detailed information on the preparation, labeling, storage, and administration of the ChAd155-RG investigational vaccine. Vaccine preparation will be performed by the site pharmacist on the same day of vaccine administration.

On vaccination days, vaccines will be allowed to thaw to room temperature and administered within 1 hour. The vaccine is administered IM over the deltoid region of the arm. Qualified medical personnel will wear gloves. During administration of the vaccine, medication and resuscitation equipment will be immediately available for the management of anaphylaxis.

In order to minimize dissemination of the recombinant vectored vaccine virus into the environment, the inoculation site will be covered with a dressing after immunization. This should absorb any virus that may leak out through the needle track. The dressing will be removed from the injection site after 30 minutes and will be disposed as Genetically Modified Organisms (GMO) waste by autoclaving, in accordance with the relevant SOP and current standard US practice.

RABAVERT Vaccine²³

The RABAVERT Vaccine will be prepared as outlined in the package insert. Additional information: See the MOP for detailed information on the preparation, labeling, storage, and administration of study vaccine for each group. Vaccine preparation will be performed by the site pharmacist on the same day of vaccine administration.

Visually inspect the ChAd155-RG Vaccine, RABAVERT Vaccine, and admixture vials, upon receipt and before use. If the vaccine(s) appear(s) to be damaged, contaminated, or discolored, contain visible particulate matter, or if there are any concerns regarding its integrity, do not use the affected vaccine(s). Instead, quarantine it at the correct storage temperature and label it "Do Not Use" (until further notice). The site PI or responsible person should immediately contact the DMID Product Support Team at [contact] and DMID CPM for further instructions before any additional vaccines are administered. Based on the information collected, DMID and/or the manufacturer will determine whether the affected vaccine(s) or admixture can be used. If it cannot be used, the site will receive specific final disposition instructions from DMID (e.g. how to return the affected vaccine(s) to DMID CMS or destroy it on site). If the vaccine(s) or admixture is unusable, the site pharmacist will prepare another dose

of admixture vial. Replacement vials may be requested by contacting DMID. Additional instructions for quarantine and DMID contact information are provided in the MOP.

Study vaccine administration will be performed by an unblinded vaccine administrator who is credentialed to administer vaccines, but will not participate in dose preparation, and may not be involved in study-related assessments, subject contact, or data collection after vaccine administration. On the assigned dosage days, each dose of vaccine will be administered to subjects via a single IM injection (depending on group assignment and/or randomization) in the preferred arm. The dose administration schedule is as follows:

- Subjects randomized to Group A will receive ChAd155-RG at the lower dosage (5×10^{10} vp) on Day 1, then placebo injections on Days 8, 15, and 22
- Subjects randomized to Group B will receive ChAd155-RG at the higher dosage (1×10^{11} vp) on Day 1, then placebo injections on Days 8, 15, and 22
- Subjects randomized to Group C will receive ChAd155-RG at the higher dosage (1×10^{11} vp) on Days 1 and 15, and placebo injections on Days 8 and 22
- Subjects randomized to Group D will receive RABAVERT at the standard dose (1mL) on Days 1, 8, and 22, and a placebo injection on Day 15

Placebo

Gently invert the normal saline vial 5 to 7 times. Using aseptic technique, puncture the septum top of the saline vial with a 1-inch, 23- or 25-gauge disposable, sterile needle attached to a 1-mL disposable, sterile syringe. Withdraw 1.0 mL from the saline vial. The prepared saline dose will be allowed to store at room temperature and administered within 1 hour. The dose will be administered IM over the deltoid region of the preferred arm.

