5.3.2. Masking Procedures

Investigators and study personnel performing any study-related assessments following vaccination will be blinded to study vaccine. Syringes will be labeled with an overlay/blinding tape containing the subject ID, and the treatment number from the treatment key, and expiration time for the syringe, and provided to the unblinded vaccine administrator. Lab personnel performing assays will be blinded to all subjects.

The randomization scheme will be generated by the Statistical and Data Coordinating Center (SDCC) and provided to unblinded study personnel (i.e., pharmacists preparing vaccines, clinical staff administering vaccines) at the site.

The unblinded vaccine administrator will be credentialed to administer vaccines, but will not be involved in study-related assessments, subject contact, or data collection following vaccination.

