#### 4.4.6. Blinding

Investigators and study personnel performing any study-related assessments following vaccination will be blinded to study vaccine. Syringes will be labeled with an overlay/blinding tape containing the subject ID, treatment number from the treatment key and expiration time for the syringe, then provided to the unblinded vaccine administrator. Lab personnel performing assays will be blinded to all subjects.

The randomization scheme will be generated by the Statistical and Data Coordinating Center (SDCC) and provided to authorized, unblinded study personnel (i.e., pharmacists preparing vaccines, clinical staff administering vaccines) at the site.

The unblinded vaccine administrator will be credentialed to administer vaccines but not involved in study-related assessments, subject contact, or data collection following vaccination.

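### Protocol 6.2 specifies a 30-minute dressing for ChAd155-RG injections only, and neither the protocol nor the SAP makes post-injection handling the same for RABAVERT and placebo, which leaves a possible visible product cue

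*Protocol*

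**What the plan says.** The dressing instruction, "the inoculation site will be covered with a dressing after immunization", appears once, in Protocol 6.2 under the ChAd155-RG heading. It has a vector-specific purpose, "In order to minimize dissemination of the recombinant vectored vaccine virus into the environment", and a fixed end: "The dressing will be removed from the injection site after 30 minutes and will be disposed as Genetically Modified Organisms (GMO) waste by autoclaving".

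The other products are handled differently in the text:

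- **RABAVERT (6.2):** no dressing is mentioned. The text defers to the package insert and the MOP: "See the MOP for detailed information on the preparation, labeling, storage, and administration of study vaccine for each group".
- **Placebo (6.2):** the preparation is described step by step and stops at the injection: "The dose will be administered IM over the deltoid region of the preferred arm". No dressing follows.

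The stated masking measures are four injections of equal volume on one schedule for everyone (Protocol 4), covered syringes (SAP 4.4.6: "Syringes will be labeled with an overlay/blinding tape containing the subject ID"; Protocol 5.3.2 has the same measure) and an unblinded administrator. After injecting, the administrator "will not be involved in study-related assessments, subject contact, or data collection following vaccination" (5.3.2) and, in 6.2, "may not be involved in study-related assessments, subject contact, or data collection after vaccine administration". No role is named to remove the dressing.

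Protocol 5.3.1 lists both the subjects and the staff who assess them after administration as blinded. The vaccination visits (7.3.1, 7.4.2, 7.4.3, 7.4.5) include at least 30 minutes of observation, the same interval as the dressing. Appendix A puts the site evaluation after 30 minutes but does not say whether the dressing is off by then.

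**The concern.** The protocol takes care to remove visible differences between arms: number of injections, volume, schedule and syringe appearance. A dressing worn for half an hour in clinic is another visible difference, and none of these measures covers it. If only ChAd155-RG recipients wear one, its presence or absence tells an informed observer which product was given.

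Two kinds of outcome depend on people who are meant to be blinded. Subjects record solicited symptoms on a memory aid (8.1). Investigators judge whether unsolicited, systemic, laboratory and serious events are related to study product (9.2.1). Those judgements define three of the primary outcome measures (3.2.1) and the SAP 9.6 tables of laboratory abnormalities related to study product. They also enter the halting rules in 9.5. The second primary objective compares ChAd155-RG with RABAVERT on safety and reactogenicity, which is the contrast a Day 1 dressing would reveal.

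**Working it through.** **Inputs.** Group sizes are from Protocol Table 1 and 11.2: A 14, B 14, C 10, D 12. The schedule is from 6.2: A and B receive ChAd155-RG on Day 1, C on Days 1 and 15, D never. The sum 14 + 14 + 10 + 12 = 50 reproduces the plan's total.

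**Dressing pattern if 6.2 is followed literally** (a dressing only with a ChAd155-RG injection):

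| Group | N | Day 1 | Day 8 | Day 15 | Day 22 |
|---|---|---|---|---|---|
| A | 14 | yes | no | no | no |
| B | 14 | yes | no | no | no |
| C | 10 | yes | no | yes | no |
| D | 12 | no | no | no | no |
| Dressings | | 38 | 0 | 10 | 0 |

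- On Day 1 the pattern separates D (12) from the other 38.
- On Day 15 it also separates C (10) from A and B. Marked by the dressing alone: 12 + 10 = 22 of 50 (44%).
- A and B (28) stay indistinguishable from each other by the dressing.
- Each sentinel stage has only one ChAd155-RG group (5.3.1). An observer who also knows the stage could place the 3 + 3 = 6 ChAd155-RG sentinels, giving 22 + 6 = 28.

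These are ceilings. They assume that every dressing is seen and its meaning known.

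**Competing cue on Day 15.** Protocol 2.3.1 reports injection-site pain in 100% of vaccine and 5.3% of placebo recipients in the earlier ChAd155 study. Suppose those rates held on Day 15, when C receives ChAd155-RG and the other 14 + 14 + 12 = 40 receive placebo:

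- Group C with pain: 10 × 1.00 = 10
- Placebo recipients with pain: 40 × 0.053 = 2.12
- Share of those with pain who are in C: 10 / (10 + 2.12) = 82.5%

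Pain would therefore already point to Group C, and the dressing adds only a modest further cue. The same calculation cannot be done for Day 1, because every group receives active vaccine and the documents give no RABAVERT pain rate.

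**Where judged relatedness enters the halting rules (9.5).** Under 9.2.1, solicited injection-site events count as related by rule, so they are left out.

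- Sentinel rules: 9 listed, 8 conditional on relatedness (all but death), less 1 solicited local = 7 of 9.
- Trial-wide rules: 11 listed, 7 conditional on relatedness, less 1 solicited local = 6 of 11.

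These counts show where the judgement is used, not that a dressing would change a decision.

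**After the fix.** With the same dressing for everyone on Days 1 and 15, all four groups have the pattern yes/no/yes/no. The dressing then identifies 0 of 50.

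**The case against.** The strongest reply is that Protocol 6.2 sends administration for each group to the MOP, where post-injection site care would naturally sit. Nothing says that RABAVERT or placebo recipients go without a dressing. Sections 5.3.1 and 5.3.2 already require blinding, so revealing handling would breach the protocol read as a whole. This stands to the extent that the MOP may settle the matter. It does not remove the gap: the only written dressing step is product-specific, its stated reason does not apply to the other products, and nothing in the protocol or SAP says how the cue is to be concealed.

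A reader might infer that 22 of 50 subjects would have their events judged by unblinded investigators. The documents do not support that. Relatedness is judged by investigators listed on Form FDA 1572 from the information available when the eCRF is completed, possibly well after the visit, and nothing places them in the room while the dressing is on. Removal before the site evaluation is the natural order under Appendix A. Section 5.3.2 also lists pharmacists as unblinded, and its bar on later subject contact is written for the administrator, so a person able to remove the dressing may exist.

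A reader might also infer a biased safety comparison. On Day 1 everyone receives active vaccine, so knowing the product does not separate active from placebo, and no direction of bias follows.

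The opposite inference, that memory aids protect the solicited symptoms, also fails. Subjects are to be blinded, and each would see their own dressing.

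**Conclusion.** The point holds as a gap in the protocol and SAP text, not as evidence that blinding failed or would fail. Taken literally, 6.2 leaves a visible product-specific cue that could mark Group D from Day 1 and Group C from Day 15. The 22 of 50 is an upper bound on exposure from the dressing pattern alone, rising to 28 if sentinel stage is also known.

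For any effect, an observer would have to see the dressing, know what it means, and then report symptoms, judge relatedness or inform the person who judges it. The added cue is modest on Day 15, if the earlier study's pain rates apply, and cannot be compared with pain on Day 1. Laboratory values and RFFIT titres do not depend on it. No size or direction of bias can be estimated.

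The conclusion rests on the MOP not already requiring uniform handling, which could not be checked. It is an inexpensive improvement, held with medium confidence.

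**What to change.** State in Protocol 5.3.2 and 6.2 that every subject receives the same visible dressing for the same wear time at least on Days 1 and 15, and that it is removed before the blinded site evaluation. If the MOP already says this, citing it in 5.3.2 is enough. No group receives ChAd155-RG on Days 8 and 22, so including those days is optional. Identical autoclave disposal is needed only if disposal is visible to blinded staff or subjects.

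The cost is one or two sentences, or a cross-reference, plus up to 12 (Group D, Day 1) + 40 (Groups A, B and D, Day 15) = 52 extra dressings. Covering all four days would need up to 200 − 48 = 152. There may be slightly more waste to autoclave. No visits are added, and the existing requirement for ChAd155-RG is unchanged.

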6.3. Accountability Procedures for the Study Investigational Product(s)

Study vaccines will be stored and shipped from DMID CMS to the site. Once received, vaccines will be stored in and dispensed by the Emory Hope Clinic Investigational Pharmacy. Unused vaccines will be returned to DMID CMS.

The FDA requires accounting for the disposition of all investigational products. After receipt of the study vaccine, the site principal investigator is responsible for ensuring that a current record of product disposition is maintained and product is dispensed only at an official study site by authorized personnel as required by applicable regulations and guidelines. Records of product

disposition, as required by federal law, consist of the date received, date administered, quantity administered, and the subject number to whom the study product was administered.

As this is a blinded study, the site principal investigator will delegate this responsibility to the unblinded site pharmacist. The unblinded site Pharmacist will be responsible for maintaining accurate records of the shipment and dispensing of the investigational product. The pharmacy records will be available for inspection by the DMID monitoring contractors, and is subject to inspection by a regulatory agency (e.g., FDA) at any time. An assigned Study Monitor will review the pharmacy records.

Unused reconstituted vaccines will be stored at [2°C-8°C for RABAVERT, ≤ -60 °C for ChAd155-RG] in the Investigational Pharmacy until trial accountability is completed. At trial termination, all unused vaccines will be disposed in accordance with the MOP following their complete accountability and monitoring.

